**Table 1. Nominal activities and permitted windows.**

Activity/endpoint	Nominal activity week	Nominal activity day	Protocol defined window, weeks	Protocol defined window, days
ART initiation	1	7	<1	<7
ART initiation	4	28	<4	<28
Study visit	26	182	22 - 30	154 - 210
TB Incidence	<30	<210	4 – 30	28 – 210
Safety events	<30	<210	0 - 30	0 - 210
Register review	>=30	>=210	>=30	>=210
Tracing	31-40		31 - 40	217 - 280
Primary outcome	22 - 40	154 - 280	22 – 40	154 – 280

## 4. Statistical principles

### 4.1 Confidence intervals and p-values

Statistical tests and confidence intervals will be two-sided. Estimates will be presented with 95% confidence intervals. P-values will be presented where appropriate. No adjustments will be made for multiple testing nor interim analyses. Interpretations will be based on the strength of evidence of effect size and consistency of results for related outcomes.

## 4.2 Adherence and protocol deviations

We are conducting a study attempting to reflect routine care with as little influence by the study activities as possible.

Deviations by routine clinical staff from procedures described in the protocol were not usually considered study deviations and did not affect the participant's retention in the trial. Participants not receiving their assigned intervention was not considered a safety risk, but was considered a protocol deviation.

Any protocol deviations as reported by the trial team or detected at the time of data cleaning or analysis will be described by arm.

## 4.3 Analysis populations

As per the protocol (2), all analyses will be done by the trial statistician using R (the R Foundation for Statistical Computing) or Stata (version 18, Stata Corporation, Austin/Texas, USA). Analysis will follow CONSORT guidelines. Primary analyses for the non-inferiority comparison will be performed on both the ITT and per protocol (PP) sets (3).

Our approaches for the primary outcome are further detailed in the context of the estimands framework in Tables 2a and 2b (4).

For secondary outcomes related to VL (achieving viral suppression defined by other thresholds), we will employ similar methods as for the primary outcome (both superiority and non-inferiority comparisons).

For the remaining secondary outcomes, we will employ similar methods as for the primary outcome but under the superiority comparison only.

**Table 2a. Estimand framework: primary outcome for superiority comparisons, resembling intention to treat approach [1].**

Estimand attribute	Definition	Comments
Population	Individuals aged 12 years or older, testing HIV-positive or known to be HIV-positive and not taking ART, with one or more TB symptoms according to WHO four-symptom screening (4WSS), who would not die from a trauma-related cause before having the endpoint measured.	Exclusion of individuals considered too ill to follow standard care (needing admission or referral, CNS symptoms, or a positive CrAg test), pregnant women, or those taking TB treatment were excluded as written in the protocol. Exclusion of individuals who die from trauma-related causes before having the endpoint measured.
Treatment conditions	Same day ART start (“ART first”) vs. ART start once TB confirmed or refuted (“TB results first”)	
Endpoint	HIV viral load measured and suppression <400 copies/mL 26 (22 – 40) weeks after enrolment and did not die from a non-trauma-related cause prior to 40 weeks.	Endpoint clarified to include those who die from a non-trauma-related cause or were LTFU without a VL measurement as “failures”, i.e. did not achieve viral suppression.
Summary measure	Risk differences. We will also report odds ratios and risk ratios.	
Handling of intercurrent events (IE) [2]		
Ineligible	“Principal stratum” approach	Individuals found to be ineligible after randomization are excluded from the analysis under the assumption that their eligibility would be independent of the randomization allocation
Failure to initiate assigned treatment according to protocol	“Treatment policy” approach	The IE are defined as 1)not offering same-day ART in the “ART first” arm and 2) offering ART start prior to completing TB investigation in the “TB results first” arm. This IE is ignored and considered part of the intention to treat strategy
Failure to initiate ART	“Treatment policy” approach	This IE applies only to the “TB results first” arm and is ignored and considered part of the intention to treat strategy.
Discontinuation of ART	“Treatment policy” approach	This IE is ignored and considered part of the intention to treat strategy.
Transfer to another facility	“Treatment policy” approach	This IE is ignored and considered part of the intention to treat strategy.
Death due to non-trauma	“While alive” approach	Those with the IE prior to VL measurement are included as failures; those with the IE after their VL measurement are included with their endpoint.
Death due to trauma	“While alive” approach	If the endpoint is measured prior to the IE, will be included.
Death due to trauma	“Principal stratum” approach	If the endpoint is not measured prior to the IE, these individuals will be excluded assuming the IE is independent of treatment allocation.

Lost to follow-up	“Composite” approach	No viral load measured. Those with the IE would be considered to have failed treatment and are therefore included as part of the endpoint definition above.
-------------------	----------------------	---

[1] Intercurrent events are post-randomization events that affect either the interpretation or existence of the outcome data associated with the clinical question of interest. . [2] Intercurrent events are post-randomization events that affect either the interpretation or existence of the outcome data associated with the clinical question of interest. [3] The case where individuals had blood drawn for a viral load test, but the test was invalid or failed will be handle with imputation if numbers allow.

**Table 2b. Estimand framework: primary outcome for non-inferiority comparison, resembling per protocol approach [1]**

Estimand attribute	Definition	Comments
Population	Individuals aged 12 years or older, testing HIV-positive or known to be HIV-positive and not taking ART, with one or more TB symptoms according to WHO four-symptom screening (4WSS), who would not die from a trauma-related cause before having the endpoint measured.	Exclusion of individuals considered too ill to follow standard care (needing admission or referral, CNS symptoms, or a positive CrAg test), pregnant women, or those taking TB treatment were excluded as written in the protocol. Exclusion of individuals who die from trauma-related causes before having the endpoint measured.
Treatment conditions	Same day ART start (“ART first”) vs. ART start once TB confirmed or refuted (“TB results first”)	
Endpoint	HIV viral load measured and suppression <400 copies/mL 26 (22 – 40) weeks after enrolment and did not die from a non-trauma-related cause prior to 40 weeks.	Endpoint clarified to include those who die from a non-trauma-related cause or were LTFU without a VL measurement as “failures”, i.e. did not achieve viral suppression.
Summary measure	Risk differences. We will also report odds ratios and risk ratios.	
Handling of intercurrent events (IE) [2]		
Ineligible	“Principal stratum” approach	Individuals found to be ineligible after randomization are excluded from the analysis under the assumption that their eligibility would be independent of the randomization allocation
Failure to initiate assigned treatment according to protocol	“Principal stratum” approach	The IE are defined as 1)not offering same-day ART in the “ART first” arm and 2) offering ART start prior to completing TB investigation in the “TB results first” arm. We are interested in the subpopulation of patients who would not experience this IE. To account for the assumption that these IE are not independent of treatment assignment, the estimator will be estimated using weighting methods (see section 6.2).
Failure to initiate ART	“Treatment policy” approach	This IE applies only to the “TB results first” arm and is ignored and considered part of the intention to treat strategy.
Discontinuation of ART	“Treatment policy” approach	This IE is ignored and considered part of the intention to treat strategy.
Transfer to another facility	“Treatment policy” approach	This IE is ignored and considered part of the intention to treat strategy.
Death due to non-trauma	“While alive” approach	Those with the IE prior to VL measurement are included as failures; those with the IE after their VL measurement are included with their endpoint.
Death due to trauma	“While alive” approach	If the endpoint is measured prior to the IE, will be included.

Death due to trauma	“Principal stratum” approach	If the endpoint is not measured prior to the IE, these individuals will be excluded assuming the IE is independent of treatment allocation.
Lost to follow-up[3]	“Composite” approach	No viral load measured. Those with the IE would be considered to have failed treatment and are therefore included as part of the endpoint definition above.

[1] Text which differs from Table 2a is shown in blue. [2] Intercurrent events are post-randomization events that affect either the interpretation or existence of the outcome data associated with the clinical question of interest. [3] The case where individuals had blood drawn for a viral load test, but the test was invalid or failed will be handle with imputation if numbers allow.

## 5. Trial population

### 5.1 Screening data

No specific screening data were captured, aside from those used to determine eligibility for the trial (see sections 3.1 and 5.2).

### 5.2 Eligibility

Screening/eligibility data will be summarized in a CONSORT flowchart, showing the total number of people screened and the reasons for screening failures as per the eligibility criteria in section 3.1. See template in section 8.

### 5.3 Recruitment

We will present graphically screening and enrolment over time. The CONSORT flowchart will include the numbers of participants randomized by arm. Enrolment will be presented by the country (stratification factor; see section 8).

### 5.4 Withdrawal/follow-up

The CONSORT flowchart will summarize each follow-up event (study visit and register reviews), by randomized arm. For participants who did not attend the study visit as expected, tracing information will be summarized.

### 5.5 Baseline patient characteristics

Baseline characteristics will be summarized by randomized group, using medians and interquartile ranges for continuous variables and numbers and percentages for categorical variables. A shell table showing the variables and categories is included in section 8. Assessment will be made for baseline imbalances between the randomization arms by visual inspection by the trial steering committee before looking at outcome data. The primary analysis will be adjusted to include any covariates so identified (erring on the side of inclusivity). There will be no formal testing of baseline characteristics across randomized groups (5,6).

## 6. Analysis

Analyses will follow CONSORT guidelines, including extensions for non-inferiority trials (6–8). Analyses will include all follow up to the date of data freeze.

Analyses will be performed by the trial statistician. There will be no independent programming of the analyses, rather we rely on the training and experience of the team for the accuracy of the data, analyses and interpretations; and the results will be assessed as a whole for consistency.

Percentages will be reported to zero decimal places, unless <0.5% when they will be given to one decimal place.

## 6.1 Outcome definitions

Here we define outcomes for analysis. Table 1 provides the analysis windows for the occurrence of the outcomes.

### TB diagnosis

A positive TB diagnosis is defined as any of the following:

- Positive Xpert MTB/RIF Ultra: positive (with or without resistance) or trace results
- chest x-ray judged suggestive of TB and requiring treatment by the responsible health care provider
- clinical judgment requiring treatment as indicated by the responsible health care provider
- positive urine TB Determine LAM (1+, 2+, 3+, 4+)

Prevalent TB: TB diagnosed through TB investigations completed up to a maximum of 28 days after enrolment

Incident TB: TB diagnosed as described above and not meeting the definition of prevalent TB.

### Primary outcome

The study visit for primary outcome assessment was scheduled together with the routine 6 month ART refill visit. Study staff tried to ensure that a VL was measured for the assessment of the study primary endpoint. If VL was not successfully measured or a study visit did not occur, participants were traced in order to obtain the outcome assessment.

Viral suppression is defined as a HIV VL <400 copies/mL during the defined analysis window of 154-280 days (Table 1). The viral load was obtained from routine laboratory reports at study facilities, from laboratory reports of referral facility in case of transfer out, or from dried blood spot (DBS) sample for participants without documented clinic visit but found during home visit tracing.

If more than one VL is available for a participant during this window, any value meeting the definition of viral suppression will be considered and defined as the participant achieving the primary endpoint.

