### **6.9 Study visit, week 26 (week 22 - 30) (routine staff and study staff)**

The study visit will be scheduled together with the routine 6 month ART refill visit. Study staff will ensure that a VL gets measured for the assessment of the study endpoint. In addition to adherence counseling and ART refill by routine staff, study staff will take a targeted clinical history including inquiry about ART and TB status, current health status, medication, adherence and possible SAEs since enrollment. Collection of two tubes of venous blood for centrifugation and storage (or a DBS if venous blood draw is not possible) and subsequent HIV genotyping and resistance testing or other related research (as specified in section 16)

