### **6.11 Tracing for outcome assessment, weeks 31 - 40 (study staff)**

Participants without a documented VL measurement at the study facility between week 22 and 30 after enrolment will be traced via phone calls and home visits if required between weeks 31 and 40 after enrolment to ascertain their outcome.

In case of documented transfer out, the referral facility will be contacted to obtain a VL laboratory report and the participants will be contacted via phone for assessment of engagement in care and possible SAEs during the follow-up period.

For participants without a documented VL between week 22 and 30 and no documented transfer out, a DBS and if possible two tubes of venous blood (may not be possible for example for household visits) for VL measurement and storage will be collected and the reasons for not having attended a clinic visit between week 22 and 30 will be inquired together with assessment of engagement in care and possible SAEs during the follow-up period. If participants are not engaged in care anymore, the study team will re-link them by giving them an appointment at the health facility.

In case participants cannot be traced back, but relatives or friends of the participants can be contacted (contacts provided by the participants at enrolment), they will be asked about the presumed outcome of the participant. If friends or relatives report a transfer out, the reported referral facility will be contacted to obtain a VL laboratory report. If a participant has died, circumstances of death (in particular whether death was due to trauma and whether TB was diagnosed prior to death) will be recorded.

**Figure 2 Flow of events SaDAPT Trial** CNS: Central nervous system, CrAg: Cryptococcal antigen, DBS: Dried blood spot, CPT: Cotrimoxazole preventive therapy, TPT: TB preventive therapy, SAE: Serious adverse event, AESI: Adverse event of special interest, VL: Viral load

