## 6.12 Schedule of events

TIMEPOINT	0 Screening enrolment	TB results	28 days Register review	Week 26 (22-30) Study visit	30 week Register review	Weeks 31-40 Tracing 
Eligibility screening	X					
Arm allocation	X					
INTERVENTION:						
ART initiation ("ART first arm")	X					
ART initiation ("TB results first arm")		X 				
ASSESSMENTS:						
Questionnaire (including brief medical history)	X			X		(X)
Brief physical examination	X			X		(X)
CD4 cell count	X					
CrAg test if CD4 <200 cells/ml or clinical indication	X					
TB investigations 	X					
Collection of plasma samples 	X			X		(X)
SAE and AESI surveillance 	(X)	(X)		(X)		
HIV Viral Load				X		(X)
Register review: Ensure complete and correct trial data by checking routine registers			X		X	
ROUTINE CARE:						
ART counselling	X	X		X		
ART refills 				X		(X)
Start TB treatment or TPT 		X				
Ongoing clinical care as required	(X)	(X)		(X)		(X)
Start CPT 	(X)					

Tracing via phone calls and home visits if no documented VL in endpoint assessment window at 22-30 weeks

 ART provision by routine services, the trial intervention is to allocate the timing of ART

 ART start if not diagnosed with TB disease, if TB disease diagnosed ART may be delayed up to 14 days— according to local routine

 According to local routine

 Or DBS if venous blood draw is not possible

 AE surveillance; participants, family members and routine staff are asked to contact study team in case of medical complaints. Referral to study team for in case of suspected SAE or TB-IRIS

 According to local routines

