#### 9.2.1 Primary analysis

The primary analysis for this study will be the comparison of viral suppression rates between the two study arms. Individuals who do not have documented VL 22 – 40 weeks after enrolment, died, transferred out without a documented VL, or were lost to follow-up will be considered to have a negative outcome (i.e., not achieved viral suppression). The analysis will use a logistic regression model adjusted for the pre-specified randomization stratification factors. Moreover, we will adjust for the most important baseline characteristics if found to be unbalanced (gender, age, ART naive vs reinitiating ART, number and type of TB symptoms) between study arms. For the non-inferiority comparison between the two arms, a CI approach will be used. A figure illustrating the confidence intervals for the risk differences and the non-inferiority margin will be presented. If the lower bound of the confidence interval for the risk difference does not include the non-inferiority margin, then the intervention will be considered non-inferior. Primary analyses for the non-inferiority comparison will be performed on the mITT, per-protocol, and complete case sets. If the “ART first” arm is found to be non-inferior to the “TB results first” arm in the mITT and per-protocol sets, then we will assess for superiority using the mITT set. Further details will be provided in the statistical analysis plan.

As a sensitivity analysis for the primary analysis, primary endpoint information obtained from the tracing visit will not be included.

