### 3.7 Timing of outcome assessments

Baseline is defined as the date of randomization. Time will be measured from randomization.

Baseline laboratory results are defined as those measured at the time of screening to a maximum of 14 days after screening. Of note, the time of a laboratory result is defined as the time when the sample was taken, not the time when the sample was processed or result available. Any laboratory tests done to establish a TB diagnosis and completed within 28 days of enrolment are considered for the establishment of prevalent TB.

Table 2 shows the nominal activity weeks and the permitted ranges as defined in the protocol, and as defined for analysis. The analysis windows are chosen to be as inclusive (wide) as possible while retaining clinical relevance, and without overlap between the windows for different activities. For the primary outcome and secondary outcomes of viral load, if there is more than one measurement recorded within the allowed time window, then any evidence of viral suppression within the window will be considered. For all other measurements and outcomes, if there is more than one measurement within a given interval, then the value will be taken that is within the protocol defined window but closest to the nominal activity day.

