### Primary outcome analysis

The primary analysis for this study will be the comparison of viral suppression rates between the two study arms. For the primary outcome, we will summarize the numbers and percentages of participants included in the analysis, and experiencing the intercurrent events, as per Tables 2a and 2b.

The analysis will use a modified Poisson regression with a log link and robust standard errors to calculate risk differences (10,11). The model will be adjusted for country, the pre-specified randomization stratification factor. (12) Moreover, we will adjust for the most important baseline characteristics (age, gender, CD4 cell count, and ART status) if found to be unbalanced between study arms. In the case of convergence issues, we will use marginal standardization to obtain the risk differences (13).

For the non-inferiority comparison between the two arms, a CI approach will be used. A figure illustrating the confidence intervals for the risk differences and the non-inferiority margin will be presented. If the lower bound of the confidence interval for the risk difference does not include the non-inferiority margin, then the intervention will be considered non-inferior.

For the non-inferiority comparison in the per-protocol analysis, we will use weighting techniques to re-weight the population (14) to account for a potential lack of exchangeability introduced by excluding individuals where the offer of ART did not follow the intervention strategy.

In addition to the absolute effect measure of risk differences, we will report the relative effect of the intervention as well with odds ratios and risk ratios as recommended by the CONSORTs statement (6).

As per section 3.4, if the intervention is found to be non-inferior to the control arm in both the ITT and per-protocol population, then we will assess for superiority under the superiority comparison approach (Table 2a) by assessing whether the 95% CI for the risk difference excludes 0.

We will conduct a complete case analysis in which only individuals with a valid VL measurement in the endpoint window of 22 to 30 weeks is included.

We will summarize what proportion of the primary outcome information came from tracing activities.

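### Does counting any suppressed viral load in weeks 22 to 40 as a success call for a one-measurement sensitivity analysis?

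*SAP*

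**What the plan says.** **The rule.** SAP 6.1 (Primary outcome) defines success as a VL below 400 copies/mL in days 154 to 280. Where several VLs fall in that window, "any value meeting the definition of viral suppression will be considered and defined as the participant achieving the primary endpoint". SAP 3.7 says the same for the primary and the secondary VL outcomes: if there is more than one measurement, "then any evidence of viral suppression within the window will be considered". For everything else that is measured repeatedly, "then the value will be taken that is within the protocol defined window but closest to the nominal activity day". Protocol 4.1.1 gives the endpoint as suppression at 26 (22 to 40) weeks and has no rule for several VLs.

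**How VLs arise.** For the week 26 visit, Protocol 6.9 states: "Study staff will ensure that a VL gets measured for the assessment of the study endpoint". After week 30, Protocol 6.11 limits tracing: "Participants without a documented VL measurement at the study facility between week 22 and 30 after enrolment will be traced". The first footnote to the schedule of events agrees: "Tracing via phone calls and home visits if no documented VL in endpoint assessment window at 22-30 weeks". Protocol 6.10 makes a final register review at 30 weeks mandatory.

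**Other analyses of the primary outcome.** SAP 6.2 plans a complete-case analysis in which "only individuals with a valid VL measurement in the endpoint window of 22 to 30 weeks is included". Protocol 9.2.1 plans a sensitivity analysis in which "primary endpoint information obtained from the tracing visit will not be included". The SAP also has other suppression thresholds, a recoding of some Malawi dried-blood-spot results, possible multiple imputation for missing VLs, and a summary of how much outcome information came from tracing.

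**The concern.** The SAP has a neutral rule for choosing among repeated values and exempts VL from it. Within one participant the exemption works in one direction only: an unsuppressed VL followed by a suppressed one becomes a success, and the reverse pair stays a success. In a non-inferiority trial this invites suspicion. If ART first truly had more unsuppressed participants, it would have more failures available for conversion, and equal repeat testing would shrink the observed deficit.

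None of the listed analyses separates this effect. The complete-case analysis changes window and population together and does not say which VL counts if two fall in weeks 22 to 30. The analysis without tracing data mostly removes first VLs and leaves routine repeats in place. The threshold analyses use the same any-value rule. The Malawi recoding changes how a result is read, not which result is used. Imputation concerns missing VLs only. If the rule moved the estimate appreciably, the planned output would not show it.

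**Working it through.** **1. The plan's own figure.** Inputs from SAP 3.3 and the Protocol synopsis: 75% in both arms, margin 10 points, one-sided alpha 0.025, power 80%.

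n per arm = (1.960 + 0.842)² × 2 × 0.75 × 0.25 / 0.10² = 7.849 × 0.375 / 0.01 = 294.3, rounded up to 295. This matches the plan. At 295 per arm the standard error is √(0.375/295) = 0.0357, so the 95% half-width is 7.0 points and power is 80.1%. One net reclassified participant is 100/295 = 0.34 points.

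**2. A model for the rule.** Let k be the share of participants with an unsuppressed single VL who also have a suppressed VL in the window, and m the share of an arm with no VL. Neither is in the documents; both are assumed. If p is the success rate on one VL, the rate under the any-value rule is p + (1 − p − m) × k.

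**3. Planning scenario.** With 75% in both arms and equal m and k, both rates rise by the same amount and the risk difference stays at zero. A common rise of 1, 2 or 3 points only lifts power slightly, to 81.2%, 82.3% or 83.4%.

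**4. At the margin.** Take 75% against 65% and m = 10% in both arms. Then control = 0.75 + 0.15k and ART first = 0.65 + 0.25k, so the difference is −10 points + 10k points.

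| k | Difference (points) | Reclassified of 295, control / ART first |
|---|---|---|
| 1% | −9.9 | 0.4 / 0.7 |
| 2% | −9.8 | 0.9 / 1.5 |
| 5% | −9.5 | 2.2 / 3.7 |
| 10% | −9.0 | 4.4 / 7.4 |

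The direction is not fixed. With k = 2% in control only, the difference is −10.3; in ART first only, −9.5. With m = 10% in control and 20% in ART first and equal k, both arms gain 0.15k and nothing moves.

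**5. A wide range.** Suppose 10% to 50% of unsuppressed participants had a repeat in the window and 30% to 60% of those repeats were suppressed. Then k runs from 0.10 × 0.30 = 3% to 0.50 × 0.60 = 30%, and the shift at the margin from 0.3 to 3.0 points. The upper end needs half of all unsuppressed participants to be retested inside the window. Nothing in the plan schedules that.

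**6. What the documents say about repeats.** One VL is scheduled, and tracing for a VL is confined to participants without a study-facility result in weeks 22 to 30. A tracing VL is therefore usually a first VL, and a second has to come from unscheduled routine testing. This supports a small k but does not fix it.

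**7. What is being compared.** The shifts above measure the distance to a different endpoint: suppression on one chosen VL. The protocol endpoint allows a VL anywhere in weeks 22 to 40. A participant unsuppressed at week 26 and suppressed at week 38 has met it. The shifts are therefore not bias in the trial's own endpoint, and an error rate computed from them would not be the trial's type I error.

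**The case for a change.** The strongest case for a change is this. The trial is open-label and routine staff know the allocation, so unscheduled repeat testing could differ by arm even though the laboratory is blinded. Second VLs have ways in: SAP section 6 takes all follow-up to the data freeze, SAP Table 1 places the register review at or after week 30, and trial participants belong to the ART initiation cohort, whose one-year register review also covers viral suppression. A net difference of about three participants is one point, against a half-width of 7.0. The check needs one derived variable, and the SAP's rule for other measurements could supply it.

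Part of this stands. No planned analysis isolates the rule, and the small number of repeats is a judgement, not a reported count. Stating by arm how many had more than one VL in the window, and how many would change status on the VL nearest day 182, would be a useful line in the report.

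The rest does not carry a change. Nothing in the plan directs different testing by arm, and the possible shift has no fixed direction. First, last or nearest VL would each be another choice; Table 1 gives the primary outcome a range and no single nominal day, so the general rule could not be applied to it without a further decision. The planned analyses also give partial cover: the complete-case analysis drops all VLs from weeks 31 to 40, and the analysis without tracing data keeps the full set and, for most participants, rests on the scheduled VL.

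**Conclusion.** No change to the plan follows. The any-value rule is stated twice in consistent terms, applies alike to both arms, rests on laboratory results processed blind to allocation, and stays within the protocol endpoint. Following the plan as written gives a sound non-inferiority conclusion for that endpoint. A one-VL analysis would leave the primary rule and the decision as they are.

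The likely size is very small: nil under the planning assumption with equal repeat testing, and 0.1 to 0.2 points at a ten-point deficit if k is 1% to 2%. Larger values need far more retesting than the schedule provides, or retesting concentrated in one arm. This rests on assumed k and m, and the documents cannot confirm them. The dated VLs can. Analysts can report the counts as a matter of routine, labelled post hoc if outcomes by arm have been seen.

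A separate matter would affect any such recount. In SAP Tables 2a and 2b the endpoint row requires no non-trauma death before 40 weeks, while the row on non-trauma death keeps a VL measured before death. Those rows need reconciling on their own account, whichever VL is used.
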